APPENDIX G continued

| Grade | | |
|--|---|--|
| Adverse Event | 3 | 4 |
| GASTROINTESTINAL continued | | |
| Mucositis Note: Radiation-related mucositis is graded as Mucositis due to radiation. | Painless erythema, edema, or ulcers preventing swallowing or requiring hydration or parenteral (or enteral) nutritional support | Severe ulceration requiring prophylactic intubation or resulting in documented aspiration pneumonia |
| Typhlitis (inflammation of the cecum) Also consider Hemorrhage/bleeding with grade 3 or 4 thrombocytopenia, Hemorrhage/bleeding without grade 3 or 4 thrombocytopenia, Hypotension, Febrile neutropenia. | Abdominal pain, diarrhea, fever, and radiographic or biopsy documentation | Perforation, bleeding or necrosis or other life-threatening complication requiring surgical intervention (e.g., colostomy) |

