| Relapse | 17 | 23 | 26 |
| TRM | 2 | 2 | 2 |

2d. Treosulfan Pharmacokinetics

Studies have demonstrated highly predictable PK in adult patients; however, limited data are available for pediatric patients. In addition, very little data is available on the relationship between treosulfan exposure and HCT outcomes including early toxicities and engraftment. Van der Stoep recently published on treosulfan pharmacokinetics and the drug's relationship with regimen-related toxicity and early clinical outcome in 77 pediatric patients with hematological malignancies (n=12) or non-malignant diseases (n=65) who underwent HCT. Conditioning consisted of treosulfan, fludarabine, +/- thiotepa (n=52) followed by HLA-matched sibling n=27, matched URD ($\geq 9/10$; n=36), or haploidentical (n=14) grafts. Hematopoietic cell sources varied and included bone marrow (n=50), PBSC (n=20), cord blood (n=6), and bone marrow plus cord blood (n=1). Van der Stoep and colleagues reported low intra-patient variability (13.9%) but high inter-patient variability [56%; <1-year old, (n=12) and 33%; ≥ 1 to 21 years of age (n=65)] among 77 pediatric patients. This is in contrast to that seen in adult patients where there is low intra- and low inter-patient variability. In addition, high treosulfan exposure ($>1650 \text{ mg}^*\text{h/L}$) was associated with an increased risk of developing grade 2 or higher mucositis [OR 4.40; 95% CI 1.19–16.28, p=0.026], increased risk of skin toxicity, including erythematous rash and skin exfoliation, [OR 4.51; 95% CI 1.07–18.93; p=0.040], and increased risk of developing multiple toxicities [OR 4.52; 95%CI 1.32–15.53, p=0.016] compared to the lower exposure ($<1350 \text{ mg}^*\text{h/L}$) group. The authors highlighted that their study included a heterogeneous group of diseases and additional data in more homogeneous and single disease groups with longer follow up are needed in order to better understand the relationship between AUC and long-term outcomes. We plan on collecting PK samples on patients enrolled on this clinical trial in order to gain a better understanding whether the exposure to treosulfan AUC for pediatric patients with nonmalignant diseases impacts engraftment and both acute and long-term toxicities. This information will help guide future studies using treosulfan-based conditioning in patients with non-malignant diseases.

3D. Fludarabine

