- b. Infants who weigh \leq 10 kg should have methotrexate dosed on a per kilogram (actual weight) basis rather than per meter squared. Therefore, the methotrexate dose is 0.5 mg/kg on Day + 1 and 0.33 mg/kg on Days +3, +6 and +11.
- c. The first dose of methotrexate should be given approximately 24 hours after completion of the initial stem cell infusion, but no sooner than 24 hours later.

2. Toxicities: In this setting, mucositis is the primary toxicity related to methotrexate. In the setting of renal or hepatic dysfunction, where there is impaired clearance of the medication, methotrexate may contribute to delayed neutrophil engraftment. Methotrexate may cause an elevation in serum transaminase.

3. Dose adjustments - Every attempt should be made to administer methotrexate as prescribed, as dose reduction or omission may increase the risk of acute GVHD. Patients at greatest risk for methotrexate -related toxicities are those with either decreased renal function or significant fluid collection (i.e. ascites, pleural effusions, etc.), where methotrexate can accumulate and, thus, delay clearance. Renal dysfunction or third space fluid accumulation are not strict contraindications to the administration of methotrexate, although dose reduction (75–50%) and rescue with leucovorin (citrovorum factor) should be considered. Similarly, while one may want to discontinue methotrexate in patients who require intubation because of severe mucositis, generally mucositis should not be a contraindication for the use of methotrexate.

4. Methotrexate levels should be monitored in patients at risk for the development of toxicity. Acceptable methotrexate levels at 24 hours or later after the administration of

methotrexate are $<0.04 \times 10^{-6}$ molar (see **Figure 3**). If toxic levels are present, leucovorin should be given per our **Standard Practice Guidelines**. The standard dose of leucovorin is 10 mg/m² IV every 6 hours.

[figure not shown]

Figure 3. Methotrexate (MTX) plasma levels and leucovorin (citrovorum) “rescue”.

Regimen B: Unrelated Umbilical Cord Blood:

All recipients of unrelated umbilical cord blood will receive prophylaxis for GVHD with 2 drugs as follows:

A. Cyclosporine A

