Adverse events will be collected and graded using the **modified (for HCT) NCI Common Toxicity Criteria (Appendix G of the protocol)**. All grade 3 and 4 adverse events (or highly unusual grade 2 adverse events), which occur from the start of study treatment (pre-transplant conditioning) through day 100 post-transplant, will be assessed by the investigator or qualified designee and recorded in the CRF, whether or not attributed to the study intervention. Adverse events that occur between the start of conditioning and day 30 will be assessed separately to identify early regimen related toxicities. The investigator should attempt to establish a diagnosis of the event on the basis of signs, symptoms and/or other clinical information. In such cases, the diagnosis should be documented as the adverse event and/or serious adverse event and not described as the individual signs or symptoms. The following information should be recorded:

- Description of the adverse event using concise medical terminology
- Description as to whether or not the adverse event is serious
- The start date (date of adverse event onset)
- The stop date (date of adverse event resolution)
- The severity (grade) of the adverse event
- A description of the potential relatedness of the adverse event to study drug or a study procedure
- The action taken due to the adverse event
- The outcome of the adverse event

The adverse event reporting in this multi-institution clinical trial will follow both the sponsor and IRB guidelines for serious adverse event (SAE) reporting. The classification of an adverse event determines what reporting procedure to follow for reporting the adverse event. (See **Table 2 and 3**).

17D: Grading of the severity of an Adverse Event

Adverse events will be graded according to CTCAE criteria. If a CTCAE criterion does not exist, the investigator should use the grade or adjectives: Grade 1 (mild), Grade 2 (moderate), Grade 3 (severe), Grade 4 (life-threatening), or Grade 5 (fatal) to describe the maximum intensity of the adverse event.

Attribution of Adverse Event

Association or relatedness to the study agent will be assessed by the investigator as follows:

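### Appendix G limits grade 3 mucositis to painless lesions, so painful, function-limiting mucositis may be under-recorded or graded differently between sites

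*Combined protocol and SAP*

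**What the plan says.** The mucositis row of Appendix G (Gastrointestinal) has two grades.

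- Grade 3: "Painless erythema, edema, or ulcers preventing swallowing or requiring hydration or parenteral (or enteral) nutritional support".
- Grade 4: "Severe ulceration requiring prophylactic intubation or resulting in documented aspiration pneumonia".

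Section 17C makes this appendix the grading instrument: "Adverse events will be collected and graded using the" "modified (for HCT) NCI Common Toxicity Criteria (Appendix G of the protocol"). It limits recording to grade 3 and 4 events, or highly unusual grade 2 events, from the start of conditioning through day 100. Section 17E repeats that limit. Section 17C adds that events from the start of conditioning to day 30 "will be assessed separately to identify early regimen related toxicities".

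Section 17D gives a different instruction: "Adverse events will be graded according to CTCAE criteria. If a CTCAE criterion does not exist, the investigator should use the grade or adjectives", followed by a generic scale on which grade 3 means severe. It states no CTCAE version.

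Mucositis is an expected toxicity. Section 15A lists it among the very common treosulfan effects (10% or more) in both adults and children. For Regimen A, Section 11 says of methotrexate: "In this setting, mucositis is the primary toxicity related to methotrexate".

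**The concern.** The functional part of the grade 3 criterion describes severe disease: the patient cannot swallow, or needs fluids or artificial feeding. Requiring the lesions to be painless works against that. It lets pain disqualify a patient from a severe grade. The Erythema multiforme row of the same appendix does the reverse and gives painful stomatitis as an example of a grade 3 finding. A wording slip is the likely explanation.

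The word matters because Appendix G decides what is written down. It has no grade 2 column, and routine grade 2 events are not recorded. An expected mucositis that falls below grade 3 would hardly count as highly unusual, so it would drop out of the adverse event record. The summaries exposed are the separate early-toxicity assessment to day 30 and the overall record to day 100, in a trial whose Introduction justifies the regimen by reduced toxicity.

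**Working it through.** The documents give no figure to reproduce, so the check applies the printed words to example records.

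**Step 1: the row on its own.** The word painless can be read in two ways. In reading A it governs all three lesion types, and the functional clause applies to all of them. In reading B painless erythema is a criterion on its own, and the functional clause applies only to ulcers.

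| Example record | Reading A | Reading B | Painless deleted, function required for all lesions | Painless replaced by painful |
|---|---|---|---|---|
| Painful ulcers, cannot swallow, parenteral nutrition, no intubation or aspiration | Neither grade | Grade 3 | Grade 3 | Grade 3 |
| Same ulcers without pain | Grade 3 | Grade 3 | Grade 3 | Neither grade |
| Painless redness, eating normally | Neither grade | Grade 3 | Neither grade | Neither grade |
| Severe painful ulceration, prophylactically intubated | Grade 4 | Grade 4 | Grade 4 | Grade 4 |

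Reading A loses the first record. Reading B keeps it, but calls trivial redness grade 3. Only the deletion, with function required throughout, sorts all four records by functional severity.

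**Step 2: other rows of Appendix G.** The gastrointestinal block has no line for other events, unlike the allergy, arrhythmia, coagulation, hemorrhage and infection blocks. The mucositis row sends radiation-related cases to a separate entry that the appendix does not contain. Under reading A, Appendix G offers the first record no other place as mucositis.

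**Step 3: Section 17C against Section 17D.** Under 17C the first record is graded by Appendix G and, on reading A, is not recorded. Under 17D it is graded by CTCAE, whose text is not in the documents. The generic scale applies only where CTCAE has no criterion, so a faulty Appendix G cell does not by itself open that route. Two sites could grade the same patient differently and each cite the protocol.

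**Step 4: size.** The documents contain no mucositis counts or grading records from this trial. The only in-document rate of grade 3 mucositis is in Section 3C (part 2a): 2 of 56 adults given treosulfan and fludarabine.

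- 2 / 56 = 3.6%.
- Section 19 expects 100 to 120 Regimen A patients: 100 × 2/56 = 3.6 and 120 × 2/56 = 4.3, or about 4 events.

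This is an illustration only. That series was in adults with hematologic malignancies, at three treosulfan dose levels, with cyclosporine-based prophylaxis and no methotrexate. The share of such events lost to the wording is unknown and could be anything from none to all.

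**The case against.** A reader might infer that severe painful mucositis fits no recorded grade and that the trial therefore miscounts a main regimen toxicity. The documents do not support that, for these reasons:

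- The gap needs reading A. On reading B, painful ulcers that prevent swallowing are grade 3.
- Section 17D offers a CTCAE route.
- Serious adverse events are defined in Section 17B without reference to toxicity grade. They include prolonged hospitalization, and Section 17G sends all of them to the sponsor, so some cases would be caught there.
- A clinician may see the intent of the row and ignore the word. No grading records show that anyone applied it literally.

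A reader might also infer that the pharmacokinetic work loses its main event. Section 3C (part 2d) does cite a published series in which high treosulfan exposure "was associated with an increased risk of developing grade 2 or higher mucositis". However, the trial's stated aim there is engraftment and acute and long-term toxicities in general, and the exploratory objective in Section 4 names only pharmacokinetic parameters. The cited association includes grade 2, which this trial does not routinely record, so correcting the word would not supply that endpoint.

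These points remove any claim of a demonstrated miscount. What stands is that the scale named in 17C, read literally, leaves out a severe form of an expected toxicity, and that 17D makes the governing rule unclear instead of repairing it.

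**Conclusion.** The grade 3 mucositis criterion is wrong as printed, because it conflicts with its own functional criteria and with another grade 3 entry in Appendix G. The consequence is a risk, not a proven error: grade 3 mucositis may be under-recorded, or graded differently between sites, in the day 30 and day 100 toxicity summaries.

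The size cannot be calculated. Under-recording depends on sites applying Appendix G rather than CTCAE and reading painless as governing all three lesion types. Inconsistency needs only that sites differ on either choice.

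The reach is limited. Mucositis is not a primary or secondary objective in Section 4. The stopping rules in Section 19 use day 200 transplant-related mortality, graft rejection, and grade III-IV GVHD in PBSC recipients. The engraftment conclusion is untouched. The correction is still worth making because it is cheap and concerns a toxicity that the protocol itself expects to be common.

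**What to change.** 1. Check the Appendix G mucositis row against its source criteria, then delete the word painless. Word the cell so that the functional clause applies to erythema, edema and ulcers alike. Do not substitute painful: that would exclude painless lesions that prevent swallowing, and the documents cannot confirm that it was intended.
2. State in Sections 17C and 17D whether Appendix G or CTCAE governs, with the version if CTCAE is used.
3. Where the printed row was applied literally, re-check mucositis grading from the start of conditioning (day -6) through day 100. Include charts that show nutritional support but no mucositis entry, since missed cases would not appear among the recorded events.

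The cost is a small edit to one cell, a sentence in Section 17, and a limited chart review if step 3 applies. No visit, test or treatment changes.

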Appendix G continued

| Grade | | |
|---|-----------------------|--|
| Adverse Event | 3 | 4 |
| HEMORRHAGE | | |
| 
Notes: Transfusion in this section refers to pRBC infusion.
 
For any bleeding with grade 3 or 4 platelets (<50,000), always grade Hemorrhage/bleeding with grade 3 or 4 thrombocytopenia. Also consider Platelets, Transfusion: pRBCs, and Transfusion: platelets in addition to grading severity by grading the site or type of bleeding.
 
If the site or type of Hemorrhage/bleeding is listed, also use the grading that incorporates the site of bleeding: NS Hemorrhage/bleeding, Hematuria, Hematemesis, Hemoptysis, Hemorrhage/bleeding with surgery, Melena/lower GI bleeding, Petechiae/purpura (Hemorrhage/bleeding into skin), Rectal bleeding/hematochezia, Vaginal bleeding.
 | | |
| Hemorrhage/bleeding with grade 3 or 4 thrombocytopenia Also consider Platelets, Hemoglobin, Transfusion: platelets, Transfusion: pRBCs, site or type of bleeding. If the site is not listed, grade as Hemorrhage – Other (Specify site, _____). Note: This adverse event must be graded for any bleeding with grade 3 or 4 thrombocytopenia. | Requiring transfusion | Catastrophic bleeding, requiring major non-elective intervention |
| Hemorrhage/bleeding without grade 3 or 4 thrombocytopenia Also consider Platelets, Hemoglobin, Transfusion: platelets, Transfusion: pRBCs, Hemorrhage – Other (Specify site, _____). Note: Bleeding in the absence of grade 3 or 4 thrombocytopenia is graded here only if the specific site or type of bleeding is not listed elsewhere in the HEMORRHAGE category. Also grade as Other in the HEMORRHAGE category. | Requiring transfusion | Catastrophic bleeding requiring major non-elective intervention |

Appendix G continued

| Grade | | |
|---|--|---|
| Adverse Event | 3 | 4 |
| HEMORRHAGE cont'd | | |
| CNS hemorrhage/bleeding | Bleeding noted on CT or other scan with no clinical consequences | Hemorrhagic stroke or hemorrhagic vascular event (CVA) with neurologic signs and symptoms |
| Hemoptysis | Requiring transfusion | Catastrophic bleeding, requiring major non-elective intervention |
| Melena/GI bleeding | Requiring transfusion | Catastrophic bleeding, requiring major non-elective intervention |
| Rectal bleeding/hematochezia | Requiring transfusion | Catastrophic bleeding, requiring major non-elective intervention |
| Vaginal bleeding | Requiring transfusion | Catastrophic bleeding, requiring major non-elective intervention |
| Hemorrhage – Other (Specify site, _____) | Requiring transfusion | Catastrophic bleeding, requiring major non-elective intervention |
| HEPATIC | | |
| Bilirubin | >3.0 – 10.0 x ULN | >10.0 x ULN |
| Bilirubin associated with graft versus host disease (GVHD) for BMT studies, if specified in the protocol. | >6 - <15 mg/100mL | >15 mg/100mL |

Appendix G continued

| Grade | | |
|--|--|---|
| Adverse Event | 3 | 4 |
| INFECTION/FEBRILE NEUTROPENIA | | |
| Febrile neutropenia (fever of unknown origin without clinically or microbiologically documented infection) | Present | Life-threatening sepsis (e.g., septic shock) |
| Infection/Febrile Neutropenia – Other (Specify, _____) | Severe | Life-threatening or disabling |
| NEUROLOGY | | |
| Aphasia, receptive and/or expressive, is graded under Speech impairment in the NEUROLOGY category. | | |
| CNS cerebrovascular ischemia | Transient ischemic event or attack (TIA) | Permanent event (e.g., cerebral vascular accident) |
| Leukoencephalopathy associated radiological findings | Severe increase in SAS; severe ventriculomegaly; near total white matter T2 hyperintensities or diffuse low attenuation (CT); focal white matter necrosis (cystic) | Severe increase in SAS; severe ventriculomegaly; diffuse low attenuation with calcification (CT); diffuse white matter necrosis (MRI) |
| Seizure(s) | Seizure(s) in which consciousness is altered | Seizures of any type which are prolonged, repetitive, or difficult to control (e.g., status epilepticus, intractable epilepsy) |
| PULMONARY | | |
| Adult Respiratory Distress Syndrome (ARDS) | - | Present |
| Apnea | Present | Requiring intubation |
| Carbon monoxide diffusion capacity (DLCO) | >25 - <50% of pretreatment or normal value | <25% of pretreatment or normal value |
| FEV1 | >25 - <50% of pretreatment or normal value | <25% of pretreatment or normal value |
| Hypoxia | Decreased O2 saturation at rest, requiring supplemental oxygen | Decreased O2 saturation, requiring pressure support (CPAP) or assisted ventilation |

Appendix G continued

| Grade | | |
|---|------------------------------------|-------------------------------------|
| Adverse Event | 3 | 4 |
| RENAL/GENITOURINARY | | |
| Creatinine Note: Adjust to age-appropriate levels for pediatric patients. | >3.0- 6.0 x ULN | >6.0 x ULN |
| Renal failure | Requiring dialysis, but reversible | Requiring dialysis and irreversible |
| SECONDARY MALIGNANCY | | |
| Secondary Malignancy – Other (Specify type, _____) excludes metastasis from initial primary | - | present |

Appendix H

The Hematopoietic Cell Transplant-Comorbidity Index (HCT-CI) 9/7/10

Assign scores appropriately if the patient has any of these comorbidities

Patient _____ (name), UPN _____ Date _____

| Comorbidities | Definitions | HCT-CI scores | Actual Lab Values/Comments |
|--|--|--|--|
| Arrhythmia | Atrial fibrillation or flutter, sick sinus syndrome, and ventricular arrhythmias requiring treatment in the patient's past history | 1 | |
| Cardiac | Coronary artery disease†, congestive heart failure, myocardial infarction in patient's past history or EF of $\leq 50\%$ at time of HCT | 1 | |
| Inflammatory bowel disease | Crohn's disease or ulcerative colitis requiring treatment in the patient's past history | 1 | |
| Diabetes | Requiring treatment with insulin or oral hypoglycemic, but not diet alone, at time of HCT | 1 | |
| Cerebro-vascular disease | Transient ischemic attack or cerebro-vascular accident in patient's past history | 1 | |
| Psychiatric disturbance | Depression/anxiety requiring psychiatric consult or treatment at time of HCT | 1 | |
| Hepatic – mild | Chronic hepatitis, Bilirubin $> \text{ULN- } 1.5 \times \text{ULN}$, or AST/ALT $> \text{ULN- } 2.5 \times \text{ULN}$ at time of HCT | 1 | |
| Obesity | Patients with a BMI of > 35 for adults or with BMI-for-age percentile of $\geq 95\text{th}$ percentile for children at time of HCT | 1 | |
| Infection | Documented infection or fever of unknown etiology requiring anti-microbial treatment before, during and after the start of conditioning regimen | 1 | |
| Rheumatologic | SLE, RA, polymyositis, mixed CTD, polymyalgia rheumatica in patient's past history | 2 | |
| Peptic ulcer | Requiring treatment in patient's past history | 2 | |
| Renal | Serum creatinine $> 2 \text{ mg/dl}$, on dialysis, or prior renal transplantation at time of HCT | 2 | |
| Moderate pulmonary | DLco and/or FEV ₁ $> 65\%-80\%$ or Dyspnea on slight activity at time of HCT | 2 | |
| Prior solid tumor | Treated at any time point in the patient's past history , excluding non-melanoma skin cancer | 3 | |
| Heart valve disease | At time of HCT excluding mitral valve prolapse | 3 | |
| Severe pulmonary | DLco and/or FEV ₁ $\leq 65\%$ or Dyspnea at rest or requiring oxygen at time of HCT | 3 | |
| Moderate/severe hepatic | Liver cirrhosis, Bilirubin $> 1.5 \times \text{ULN}$, or AST/ALT $> 2.5 \times \text{ULN}$ at time of HCT | 3 | |
| Please provide (KPS): Karnofsky Performance Score = _____ % | | Total Score $= \underline{\hspace{1cm}}$ | Signature of Provider: |

†One or more vessel-coronary artery stenosis, requiring medical treatment, stent, or bypass graft. EF indicates ejection fraction; ULN, upper limit of normal; SLE, systemic lupus erythematosus; RA, rheumatoid arthritis; CTD, connective tissue disease; DLco, diffusion capacity of carbon monoxide; FEV₁, forced expiratory volume in one second; AST, aspartate aminotransferase; ALT, alanine aminotransferase.

